9.2 Recording and reporting Safety Information

During the course of this study, i.e. from signing the informed consent onwards until the end of the last follow-up visit, all SAEs, Endpoint Events and certain non-serious AEs which occurred until 3 months after study start dose are to be collected, documented, and reported by the Investigator in the applicable eCRF's following below "safety reporting flow chart":

Figure 4: Safety reporting flow chart

How to assess Safety Events (AEs, SAEs and SUSARs)

Seriousness, severity and causality need to be assessed by the Principal Investigator or the physician to whom this activity is delegated to.

An adverse event is defined as a serious adverse event if the event is any untoward medical occurrence that at any dose:

- Results in death
- Is life-threatening
- Requires inpatient hospitalization or prolongation of existing hospitalization
- Results in persistent or significant disability/incapacity
- Is a congenital anomaly/birth defect, or
- Is an important medical event.

Note: The term “life-threatening” in the definition of serious refers to an event in which the subject was at risk of death at the time of the event; it does not refer to an event which hypothetically might have caused death if it were more severe

The following definitions should be used **to assess intensity of adverse events**:

- Mild: Awareness of sign or symptom, but easily tolerated, i.e., does not interfere with subject's usual function.
- Moderate: Discomfort enough to cause interference with usual activity.
- Severe: Incapacitating with inability to work or do usual activity, i.e., interferes significantly with subject's usual function.

Severity vs. Seriousness: Severity is used to describe the intensity of a specific event whereas the event itself, however, may be of relatively minor medical significance (such as severe headache). This is not the same as "seriousness," which is based on subject/event outcome at the time of the event.

The Investigator should **assess causal relationship between an adverse event and the study drug on the basis of his/her clinical judgment, the latest SmPC (see section 8.3) and the following definitions**. The causality assessment must be made based on the available information and can be updated as new information becomes available.

Related:

The AE follows a reasonable temporal sequence from study drug administration, and cannot be reasonably explained by the subject's clinical state or other factors (e.g., disease under study, concurrent diseases, and concomitant medications).

or

The AE follows a reasonable temporal sequence from study drug administration, and is a known reaction to the drug under study or its chemical group, or is predicted by known pharmacology.

Not Related:

The AE does not follow a reasonable sequence from study drug administration, or can be reasonably explained by the subject's clinical state or other factors (e.g., disease under study, concurrent diseases, and concomitant medications).

Recording and reporting non-serious Adverse Events (AEs)

AEs may be directly observed, reported spontaneously by the subject or by questioning the subject at each study visit. The Investigator must assess these AEs to determine seriousness, severity, and causality, in accordance with below definitions. The Investigator's assessment must be clearly documented in the site's source documentation. For the purposes of this study **non-serious AEs that are related to the IMP or non-serious AEs that occur in the cardiovascular system or non-serious AEs events involving imbalance of serum electrolytes (restricted to K⁺, Na⁺, HCO₃) will be collected in the eCRF throughout the study.**

Recording and reporting of SAEs AND SUSARs

All SAEs and SUSARs will be collected throughout the study duration. Reporting of these events to the sponsor will occur on the eCRF AE page.

Reporting of SAEs and SUSARs is mandatory and should start;

- For SAEs, from consent
- For SUSARs, from 1st IMP dose

If the SAE is unexpected, i.e., the event is not previously documented as 'expected', and is thought to be related to the study drug, this event is considered a Suspected Unexpected Serious Adverse Reaction (SUSAR).

Where a participant withdraws consent for further processing of data, this does not preclude the reporting of SAEs and SUSARs which are required to continue being reported according to the protocol for regulatory purposes.

In all cases SAEs should be reported to the Sponsor in the eCRF. **Only in case the investigator is of the opinion that the SAE is a SUSAR, the investigator needs to inform the sponsor within 24 hours after awareness of the event.** Assessment of seriousness, causality and expectedness for trials involving IMPs will be made by the PI or another authorised doctor. If an authorised doctor from the reporting site is unavailable, initial reports without causality and expectedness assessment should be submitted to the Sponsor, but must be followed-up by medical assessment as soon as possible thereafter.

For each SUSAR the following information will need to be collected:

- full details in medical terms and case description
- event duration (start and end dates, if applicable)
- action taken
- outcome
- seriousness criteria
- causality (i.e. relatedness to trial drug / investigation), in the opinion of the investigator
- whether the event would be considered expected or unexpected.

All SAEs assigned by the PI or delegate (or following central review) as both suspected to be related to IMP-treatment and unexpected will be classified as SUSARs and will be subject to expedited reporting to the Federal agency for medicines and health products (FAMHP). The Sponsor will inform the FAMHP, the EC and the Marketing Authorisation Holder of SUSARs within the required expedited reporting timescales.

Endpoints

The following events will need to be marked as an “endpoint event” in the eCRF:

- All-cause mortality: All deaths from any cause. This includes all cardiovascular and non-cardiovascular deaths.

Cardiovascular death: Death fulfilling any of the following criteria:

- Death due to proximate cardiac cause (e.g. myocardial infarction, cardiac tamponade, worsening heart failure)
- Death caused by non-coronary vascular conditions such as neurological events, pulmonary embolism, ruptured aortic aneurysm, dissecting aneurysm, or other vascular disease
- All procedure-related deaths, including those related to a complication of the procedure or treatment for a complication of the procedure (e.g. surgical or non-surgical revascularisation)
- All valve-related deaths including structural or non-structural valve dysfunction or other valve related adverse events
- Sudden death or unwitnessed death
- Death of unknown cause

Non-cardiovascular death: any death that is not thought to be due to a cardiovascular cause

- Rehospitalisation for heart failure is defined as either a hospital admission or an unscheduled contact at the emergency department for worsening HF if the patient is treated with intravenous loop diuretics.
- Rehospitalisation for a cardiac event
- Need for Renal replacement therapy: ultrafiltration or dialysis

Submit complete endpoint package within 30 days of awareness to the sponsor. This package should include anonymized source documents (SDs) relevant to the endpoint reported (e.g. discharge letter, emergency room notes, etc). The SD should include at least the reason for admission/death and the received treatment for the event (if applicable). The original SD need to be retained at the site.

Identifying a pregnancy

All pre- menopausal women who are not surgically sterile, as well as women of childbearing potential will have pregnancy urine tests performed at screening phase (Day 1). A positive pregnancy test at day 1 constitutes in screen failure.

9.3 Responsibilities

Principal Investigator (PI):

Checking for AEs when participants attend for treatment / follow-up.

1. Using medical judgement in assigning seriousness, causality and expectedness using the Reference Safety Information approved for the trial.
2. Ensuring that all SAEs and SUSARs are recorded in the eCRF. Ensure that only SUSARs are reported to the Sponsor and the Chief Investigator within 24 hours of becoming aware of the event and provide further follow-up information as soon as available.
3. Ensuring that AEs are recorded and reported to the Sponsor and the Chief Investigator in line with the requirements of the protocol.

Chief Investigator (CI) / delegate or independent clinical reviewer:

1. Clinical oversight of the safety of patients participating in the trial, including an ongoing review of the risk / benefit.
2. Using medical judgement in assigning seriousness, causality and expectedness of SAEs where it has not been possible to obtain local medical assessment.
3. Immediate review of all SUSARs.
4. Review of specific SAEs in accordance with the trial risk assessment and protocol as detailed in the Trial Monitoring Plan.
5. Assigning Medical Dictionary for Regulatory Activities (MedDRA) or Body System coding to all SAEs.
6. Preparing the clinical sections and final sign off of the Development Safety Update Report (DSUR).

Sponsor:

1. Central data collection and verification of AEs, SAEs, and SUSARs according to the trial protocol onto a safety database.
2. Reporting safety information to the CI, delegate or independent clinical reviewer for the ongoing assessment of the risk / benefit according to the Trial Monitoring Plan.
3. Reporting safety information to the independent oversight committee identified for the trial (Trial Steering Committee (TSC)) according to the Trial Monitoring Plan.
4. Expedited reporting of SUSARs to the Competent Authority (FAMHP IN be) and EC within required timelines.
5. Notifying Investigators of SUSARs that occur within the trial.
6. The unblinding of a participant for the purpose of expedited SUSAR reporting.
7. Checking for (annually) and notifying PIs of updates to the Reference Safety Information for the trial.

8. Preparing standard tables and other relevant information for the DSUR in collaboration with the CI and ensuring timely submission to the FAMHP and EC.

Trial Steering Committee (TSC):

In accordance with the Trial Terms of Reference for the TSC, periodically reviewing safety data.

9.4 Notification of deaths

All deaths will be reported to the sponsor within 5 working days of the research staff becoming aware of the event with coding of the reason of death (HF related, non-HF related, unknown). In case the death is deemed related to the IMP the event will need to be reported within 24 hours of awareness of the event.

9.5 Reporting urgent safety measures

If any urgent safety measures are taken the CI/Sponsor shall immediately and in any event no later than 3 days from the date the measures are taken, give written notice to the FAMHP and the relevant EC of the measures taken and the circumstances giving rise to those measures.

9.6 The type and duration of the follow-up of subjects after adverse events

Once an adverse event is detected, it should be followed until its resolution or until it is judged to be permanent, and assessment should be made at each visit (or more frequently, if necessary) of any changes in severity, the suspected relationship to the study treatment, the interventions required to treat it, and the outcome.

All SUSARs occurring from the time of the start of trial treatment until end of follow-up study phase (3 months) must be recorded in the eCRF within 24 hours of the investigational staff becoming aware of the event.

9.7 Development safety update reports

The CI will provide (in addition to the expedited reporting above) DSURs once a year throughout the clinical trial, or on request, to the Competent Authority (FAMHP in Belgium), Ethics Committee and Sponsor.

The report will be submitted within 60 days of the Developmental International Birth Date (DIBD) of the trial each year until the trial is declared ended

10 STATISTICS AND DATA ANALYSIS

The statistical analysis been planned together with [name] and [name] from CenStat - University Hasselt.

10.1 Sample size calculation

The ADVOR study is powered for primary end-point which is the most relevant end-point with respect to the study hypothesis and reliable data from large randomized clinical trials are available to make a formal power calculation.

In the DOSE trial, which recruited a similar study population as targeted in the ADVOR study, successful decongestion with a similar definition was approximately 11% vs 18% after 72 h in the low vs high-dose loop diuretics arm.²⁵ The high-dose loop diuretics arm of the DOSE trial is quite comparable to the standard of care group in the ADVOR study as the loop diuretic dose used in the latter is only slightly lower (2x instead of 2.5x the oral maintenance outpatient dose) and non-loop diuretics, which were infrequently used in the DOSE trial, are not allowed. Because of these slight differences, 15% is chosen as an estimate for occurrence of the primary end-point in the monotherapy with high-dose loop diuretics (SOC) group.

No reliable data are available from large clinical trials to estimate occurrence of the primary end-point in the acetazolamide arm of the ADVOR study. Therefore, after thorough discussion with the advisory board as well as with [name] / [name] (KCE Trials) a success rate of 25% was chosen, which represents a clear meaningful benefit of 10% more patients with appropriate decongestion after 72 h. Using both estimates, considering a type I error rate $\alpha=0.05$ and type II error rate $\beta=0.20$ (yielding a statistical power of 80%), the targeted sample size for the ADVOR study is calculated at $n = 494$. A 5% drop out has been calculated in order to estimate the total number of 519 patients to be enrolled in the study.

10.2 Planned recruitment rate

Patients will be recruited by approximately 24 Belgian sites within a period of approximately 24 months. The recruitment rate will start slow due to the site initiation activities at each center, which are performed in parallel during the first recruitment months. The inclusion criteria have been widened so almost all decompensated HF patients with volume overload might be suitable study candidates, which should lead to an easy recruitment of patients. In case recruitment would be lower than expected, the number of participating centers can be increased. Also, with the publication of three-monthly research letters to the participating sites and announcement through posters/leaflets of the ADVOR-study in the outpatient cardiology department, the inclusion process might be enhanced.

10.3 Statistical analysis plan

- The treatment effect for the primary end-point [Treatment success (decongestion achieved) on morning of day 4 without escalating diuretic strategy (doubling loop diuretic dose, addition of chlorthalidone, or ultrafiltration) during IV diuretic therapy on morning of day 3] is evaluated by means of a generalized linear mixed model. The statistical model will include a fixed treatment effect and random center effect.
- For the first secondary end-point [occurrence of the combined endpoint of all-cause mortality and heart failure readmission during 3 months of follow-up], a generalized linear mixed model for a binary outcome will be used. The model will incorporate a fixed treatment effect and random center effect. If the treatment effect on the composite endpoint of 'all-cause mortality and HF readmission' turns out to be statistically significant, both components will be evaluated separately in a hierarchical fashion with HF readmissions first and all-cause mortality second. For this analysis, HF readmission will include patient dying from HF during the 3 months of FU. As a sensitivity analysis the worst case scenario, assuming a HF readmission for all patients dying to non HF related causes during the 3 month follow-up will be executed.
- Length of index hospitalization and change in quality of life scores are compared among treatment arms with a linear mixed model (fixed treatment effect and random center effect). Transformation will be employed when the model assumptions (such normality) are violated.
- All hypothesis are 2-sided and tested with a significance level of $\alpha=0.05$.

The proposed statistical models all assume the missing data mechanism to be missing at random. To investigate the sensitivity of the conclusions with respect to this assumption, a sensitivity analysis by means of multiple imputation technique will be performed.

Secondary Analysis:

- All statistical models discussed in the secondary analysis include a fixed treatment effect and random effect for the center, and in case of longitudinal outcome random patient effects (intercept, slope).
- The mixed models for the primary and secondary end-point analyses will be extended with explanatory variables (such as gender, age, race, ethnicity, kidney function, neurohumoral blockers, diuretics and blood pressure)
- For the end-points collected repeatedly over time, the rate of change will be investigated using longitudinal data models.
- In case patients are re-hospitalized more than once for the same reason, i.e. HF readmission, models for recurrent events will be employed.
- To study the treatment effect on the evolution of a patient's weight a mixed model for repeated measurements data will be used. The two treatment arms will also be compared for the area under the weight curve using an ANOVA model.

- For the first secondary end-point [time till combined endpoint of all-cause mortality and heart failure readmission during 3 months of follow-up], the Kaplan-Meier method will also be used to construct survival curves for both treatment arms. A mixed effects Cox proportional hazard model, with a fixed treatment effect and random center effect is used to investigate the treatment effect for this endpoint. The Hazard ratio with a 95% confidence interval will be obtained. The appropriateness of the proportional hazard assumption will be examined.
- For the primary and secondary endpoint subgroups analysis, with subgroups defined on the basis of LVEF, will also be performed.

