7.2 Consent

The Principal Investigator (PI) retains overall responsibility for the informed consent of participants at their site and must ensure that any person delegated responsibility to participate in the informed consent process is duly authorised, trained and competent to participate according to the ethically approved protocol, principles of Good Clinical Practice (GCP) and Declaration of Helsinki. If delegation of consent is acceptable then details should be provided.

Informed consent must be obtained prior to the participant undergoing procedures that are specifically for the purposes of the trial and are outside of standard routine care at the participating site (including the collection of identifiable participant). In case the patient agrees to participate in the optional laboratory sub-study, an additional signed and dated informed consent must be obtained before the laboratory sub-study blood and urine samples will be collected.

The right of a participant to refuse participation without giving reasons must be respected.

The participant must remain free to withdraw at any time from the trial without giving reasons and without prejudicing his/her further treatment and will be provided with a contact point where he/she may obtain further information about the trial. Where a participant is required to re-consent or new information is required to be provided to a participant it is the responsibility of the PI to ensure this is done in a timely manner.

The PI takes responsibility for ensuring that all vulnerable patients are protected and participate voluntarily in an environment free from coercion or undue influence.

Eligible patients may only be included in the study after providing written (witnessed, where required by law or regulation), Independent Ethics Committee (IEC) approved informed consent or if patient is incapable of doing so, after such consent has been provided by a legally acceptable representative(s) of the patient. In cases the patient's representative gives consent, the patient should be informed about the study to the extent possible given his/her understanding. If the patient is capable of doing so, he/she should indicate assent by personally signing and dating the written informed consent document.

The process of obtaining informed consent should be documented in the patient source documents.

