7.6 Screening phase assessments

Screening testing will occur after the consent process has been finalized. The screening data gathering needs to be performed prior to the administration of the study diuretic agents. The following assessments are required and data need to be collected:

- Obtain written informed consent
- Check inclusion and exclusion criteria
- Collect demographics (collect age, gender, race and ethnicity)
- Collect medical history and notification of LVEF
- Collect concomitant medication ([see Appendix 5](#))
- Collect vital signs including body weight, arterial blood pressure and heart rate
- EQ-5D patient questionnaire to be completed by the patient ([Appendix 2 and 3](#))
- Perform volume assessment by the Principal Investigator or a Sub-investigator who has been trained in the study volume assessment. Volume assessment is based on the presence of oedema, ascites, pleural effusion (Figure 3 in section 8).
- Collect blood sample for local laboratory assessment: serum hemoglobin, hematocrit, electrolytes (Na, K, Cl, HCO₃), serum osmolality, serum urea, serum Cr, total protein, serum albumin, Fe, ferritin, TSAT, LDH, troponin, eGFR and plasma BNP or NT-proBNP
 - In a subset of randomized patients participating in the laboratory sub-study blood collected during screening will be shipped to the University Biobank Limburg ([see section 7.10](#))
- Perform pregnancy urine test (applicable for all pre- menopausal women who are not surgically sterile)
- Randomization ([see section 7.3](#))

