5.5 Data sets to be analysed

For the *primary endpoint* the statistical analysis will be based on an intention-to-treat analysis set (ITTAS) including all randomized patients. Patients will be analysed according to the treatment group they were allocated to according to the electronic randomization system (irrespective of the actual treatment received).

For the *secondary endpoints* the statistical analyses will be based on the same data set as will be used for the primary endpoint analysis.

For the *safety endpoints*, all patients that were randomized and received at least 1 dose of the investigated drug or placebo will be included (safety population). For the safety analysis, patients will be grouped based on the actual study treatment received.

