5.10.3 Treatment of missing data

The proposed statistical model assumes the missing data mechanism to be missing at random. If the level of missing data for the primary outcome in the ITTAS populations exceeds 5%, a sensitivity analysis to assess the robustness of the analysis of the primary outcome by means of multiple imputation technique will be performed for the primary endpoint.

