For each treatment arm mean, median and interquartile range for length of index hospitalization will be presented for patients who survived to hospital discharge. The effect of treatment on length of index hospitalization, for patients who survived to hospital discharge, is compared among treatment arms with a linear mixed model⁸ (fixed treatment effect and random centre effect). A log transformation will be employed as the model assumptions (such normality) will likely be violated. Model assumptions will be investigated by means of diagnostic plots. The results of this model will be presented as (geometric) mean length of index hospitalization (and 95% CI) per treatment group, the geometric mean ratio (GMR), 95% CI and associated p value.

To assess whether the treatment effect differs according subgroups defined on the basis of LVEF (see table in section 5.10.2) a subgroup analysis will be performed. The statistical model formulated for the analysis of this endpoint will be extended to include a fixed effect for the subgroup and an interaction term between the study arm and the subgroup. The interaction term will be considered significant at the 5% level. Within each subgroup, summary statistics of the outcome by treatment arm will be presented; the GMR for the treatment effect and 95% confidence interval. A p-value for the interaction test will also be reported.

5.11.3 Secondary outcome 3

The QoL scores (EQ-5D total score and EQ-VAS) will be presented using line plots for each study arm to illustrate trends over time. Depending on the distribution of the data, the means and 95% CI of means or medians and inter-quartile ranges at baseline, the morning of day 4 or discharge (whatever comes first), and at 3 months of follow up will be reported. Evolution in the QoL will be investigated via a linear mixed model, with the QoL score of morning of day 4 or discharge (whatever comes first), and 3 months follow up as the longitudinal dependent variable, with a fixed treatment effect, day, the interaction of treatment by day, and baseline QoL, random centre effect and random patient effect (intercept, slope) will be used. Model assumptions will be investigated by means of diagnostic plots. Transformation will be employed when the model assumptions (such normality) are violated.

The analysis will be performed following the recommendations of the Belgian guidelines for health economic evaluation to value health care resource use will be used:

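### SAP 5.11.3 enters baseline EQ-5D as a covariate, so the main quality-of-life analysis drops patients who have follow-up scores but no baseline

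*Combined protocol and SAP*

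**What the plan says.** **Protocol 10.3 (same text in v1.0 and v2.0).** "Length of index hospitalization and change in quality of life scores are compared among treatment arms with a linear mixed model", with fixed treatment and random centre effects. The section adds that all proposed models assume missing at random, and that multiple imputation will be used as a sensitivity analysis. It does not limit that analysis to one endpoint.

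**SAP v2.0, 5.11.3.** This is the operative model. Only the two later scores are outcomes; the SAP sets the analysis up "with the QoL score of morning of day 4 or discharge (whatever comes first), and 3 months follow up as the longitudinal dependent variable". Baseline appears instead among the terms on the right-hand side, where the SAP describes a model "with a fixed treatment effect, day, the interaction of treatment by day, and baseline QoL, random centre effect and random patient effect". The patient effect has two parts, one for level and one for trend over time. Baseline is therefore a regressor, not an outcome.

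**SAP v2.0, 5.5.** The primary analysis set is all randomised patients. For the secondary endpoints, "the statistical analyses will be based on the same data set as will be used for the primary endpoint analysis".

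**SAP v2.0, 5.10.3.** If more than 5% of primary outcomes are missing, a sensitivity analysis "by means of multiple imputation technique will be performed for the primary endpoint". Neither the SAP nor the protocol has a rule for a missing baseline EQ-5D.

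**How the baseline is collected.** Protocol v2.0 section 7.6 lists "EQ-5D patient questionnaire to be completed by the patient" among the screening assessments, and screening data are to be gathered before the study diuretics. Protocol v2.0 section 3.5 and SAP 4.1.3 allow completion from screening up to day 1, which is the dosing day. Section 7.2 lets patients who cannot consent enter "after such consent has been provided by a legally acceptable representative(s) of the patient".

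**The concern.** A likelihood-based mixed model under missing at random keeps a patient whose outcome is missing at one visit. It does not extend that to a missing covariate: by default, any row without the covariate is deleted. Baseline EQ-5D is constant within a patient, so all of that patient's rows go. Someone with observed scores at both day 4 and 3 months but no baseline adds nothing to the main analysis of the third secondary endpoint.

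Some missing baselines are foreseeable. The form is completed by the patient, around an admission that may be an emergency, and patients unable to consent may be enrolled.

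Two things are at stake: precision, because observed follow-up data are discarded, and the population, because the analysed patients become those with a baseline questionnaire rather than the all-randomised set named in SAP 5.5.

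**Working it through.** **Plan figures.** The plan gives no sample size, power or precision for EQ-5D, so there is nothing to reproduce on this endpoint. The denominator used here is the planned enrolment: 494 × 1.05 = 518.7, or 519.

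**Assumed inputs.** Neither of these is in the documents.
- Share of patients with no baseline EQ-5D, f: 5%, 10%, 20%.
- Correlation between baseline and follow-up score, ρ: 0.5, with a range of 0.3 to 0.7.

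**Step 1: who is dropped.** In one simulated data set of 519 patients with two complete follow-up visits and a 10% chance of a missing baseline, 56 patients had no baseline. The model with baseline as covariate used 463 patients and 926 of 1,038 follow-up scores. A model with baseline in the response vector used all 519 patients and all 1,038 follow-up scores.

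**Step 2: cost compared with complete baselines.** Information falls in proportion to 1 − f, so the standard error is multiplied by 1/√(1 − f).

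**Step 3: what can be recovered.** With baseline adjustment the residual variance is σ²(1 − ρ²); without it, σ². Relative to an adjusted patient, a patient without baseline therefore carries information 1 − ρ². The standard error after keeping these patients, divided by that of the planned model, is

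√[ (1 − f) / ((1 − f) + f(1 − ρ²)) ].

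At f = 0.20 and ρ = 0.5: √[0.80 / (0.80 + 0.20 × 0.75)] = √(0.80/0.95) = 0.918, a reduction of 8.2%. A simulation with n = 494 at these values gave 7.8%.

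**Step 4: if only half of those without baseline have a follow-up score.** Replace f(1 − ρ²) by (f/2)(1 − ρ²). At f = 0.20: √(0.80/0.875) = 0.956, a reduction of 4.4%.

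| Missing baseline | Patients of 519 | SE increase vs complete baselines | SE reduction if kept, ρ = 0.5 | Same, half with follow-up |
|---|---|---|---|---|
| 5% | 26 | 2.6% | 1.9% | 1.0% |
| 10% | 52 | 5.4% | 3.9% | 2.0% |
| 20% | 104 | 11.8% | 8.2% | 4.4% |

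For ρ from 0.3 to 0.7, the step 3 reduction runs from 1.3% (f = 5%, ρ = 0.7) to 9.7% (f = 20%, ρ = 0.3). The third column is not what the fix recovers, because a missing baseline stays missing. The recoverable part is in the last two columns.

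**The case against.** **Nothing in the plan recovers these patients.** A reader might infer this, and the documents do not support it. Protocol 10.3 plans a multiple-imputation sensitivity analysis for its models in general. It also plans longitudinal rate-of-change models for repeated endpoints, which could hold baseline as an outcome. What stands is narrower: the imputation is a sensitivity analysis, the SAP details it only for the primary endpoint, and the quality-of-life model that the SAP specifies has baseline on the right-hand side.

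**The sickest patients are left out, or the arms are biased.** This too is tempting and is not shown. Self-completion and consent by representative make it plausible that very ill patients lack a baseline, but no frequency is given. A form missing before dosing cannot reflect a treatment effect, so a difference between arms does not follow.

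**SAP 5.5 is flatly contradicted.** This is too strong. Section 5.5 defines who is eligible and how patients are grouped. SAP 5.1 asks for the number analysed by arm for each outcome, so it expects numbers to vary. Patients with no EQ-5D at all stay out under any model. What stands is that patients who do have outcome data are removed by a modelling choice that can be avoided.

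**The gain is small and the endpoint is exploratory.** Both are fair. SAP 5.3 treats everything except the primary endpoint as exploratory. Baseline adjustment is standard practice, the window up to day 1 gives some time to complete the form, and patients too ill for the baseline form may also miss day 4. If baselines are nearly complete, the gain is close to zero.

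**Part of the reporting is already planned.** SAP Appendix A lists the number and percentage with baseline EQ-5D by arm. It does not separate questionnaires completed before the first dose from later ones.

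**Conclusion.** The point holds for the main quality-of-life analysis in SAP 5.11.3. As written, it discards all observed follow-up scores of any patient without a baseline EQ-5D, and no rule in the SAP prevents this. The harm is to precision and to the breadth of the analysed population; no distortion of the treatment comparison has been demonstrated.

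The size rests on assumptions. At 5-20% missing and a correlation of 0.5, the recoverable reduction in standard error is at most about 2-8%. It is about 1-4% if half of these patients also lack a follow-up score. The deletion itself is the default behaviour of such models; the SAP does not state it, but it follows from the model and the missing rule. This is a worthwhile, low-cost improvement to an exploratory secondary endpoint and does not touch the primary analysis.

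**What to change.** Amend SAP 5.11.3 in one of two ways.

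1. Preferred: put pre-dose baseline EQ-5D in the response vector with the two follow-up scores. Constrain the baseline mean to be equal in both arms and estimate the treatment effect at each follow-up visit (constrained longitudinal data analysis). Every randomised patient with at least one EQ-5D value then enters the model.
2. Alternatively, keep the planned model and replace a missing baseline by the overall baseline mean across both arms, adding a missing-indicator as a covariate.

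Apply the same rule to the index value and the EQ-VAS.

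Both options need a baseline that treatment cannot have influenced. Because the window runs up to day 1 without saying that the form must precede dosing, the SAP should treat a questionnaire completed after the first study dose as a missing baseline. It should also report, by arm, the number without a pre-dose baseline.

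The cost is SAP wording, slightly more SAS code, and a check of questionnaire timing against the first dose. No new data or patients are needed. With complete pre-dose baselines, the result is essentially the planned baseline-adjusted estimate.
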